### 5.1.2 Secondary Efficacy Endpoints

The secondary efficacy endpoints of TTNT, DMFS, ORR and QoL using the EQ-5D-5L or EQ-5D-Y will be compared between treatment arms.

#### 5.1.2.1 Time to Next Treatment (TTNT)

TTNT is defined as the time from randomization to the start of post-study treatment subsequent intervention:

[TTNT = start date of subsequent intervention – randomization date + 1].

Subsequent intervention includes anticancer therapy, cancer-related surgery and local regional therapy. Subjects who do not start any post-study treatment intervention will be censored at their last known date of being alive (same as OS).

#### 5.1.2.2 Distant Metastasis-Free Survival (DMFS)

DMFS is defined as the time from randomization to evidence of a new distant metastasis not documented at time of randomization:

[DMFS = a new distant metastasis documented date – randomization date + 1].

Subjects who do not have any new distant metastasis will be censored at their last tumor assessment.

#### 5.1.2.3 Objective Response Rate (ORR)

The ORR is defined as the percent of subjects who achieve either CR or PR per RECIST1.1 by investigator's assessment as best response:

[ORR = (CR+PR)/total number of subjects].

The best overall response is determined once all the data for the subject is known. No confirmatory measurement for CR or PR is required in this study. The best overall response is defined as the best response (in the order of CR, PR, SD, and PD) among all overall responses recorded from randomization until the last radiographic tumor assessment (for example, a subject who has SD at first assessment, PR at second assessment, and PD on last assessment has a best overall response of PR). All tumor assessments after the first PD will be ignored.

ORR by independent radiological review, if required, will be the supportive endpoints and its definition and censorship are similar to the ORR by investigator's assessment defined above.

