4. Must have documentation of no evidence of disease progression of the tumor during or after completion of first line systemic anti-cancer therapy as determined by the investigator using RECIST v1.1 guidelines. Subjects who have a tumor response of SD with evidence of \geq 15% to 20% increase in tumor burden will be submitted for Central Review to adjudicate the investigator's assessment of tumor response prior to randomization. Subjects with NED are eligible.
 5. Have an Eastern Cooperative Oncology Group (ECOG) performance status of 0 or 1.
 6. Age \geq 12 years.
 7. Have a life expectancy of at least 6 months, as determined by the investigator.
 8. If a female of child-bearing potential (FCBP), willing to undergo pregnancy testing and agree to use at least 1 highly-effective contraceptive method, such methods include combined estrogen and progesterone-containing hormonal contraception associated with inhibition of ovulation (oral, intravaginal, transdermal) or progesterone only hormonal contraception associated with inhibition of ovulation (oral, injectable, implantable), intrauterine device (IUD), intrauterine hormone-releasing system (IUS), bilateral tubal occlusion, vasectomized partner or true sexual abstinence (when this is in line with the preferred and usual lifestyle of the subject, refraining from heterosexual intercourse during the entire period of risk associated with study treatments) during the dosing period and for 1 month (which is the duration of a menstruation cycle) after administration of the last dose of CMB305. More stringent contraception criteria should be followed if requested by local regulatory authorities.
 9. If male and sexually active with a FCBP, must be surgically sterile (i.e., vasectomy) or agree to use highly-effective contraception, such as latex condom, during the dosing period and for 3 months (which is the duration of a sperm cycle) after administration of the last dose of CMB305. More stringent contraception criteria should be followed if requested by local regulatory authorities.
 10. Have recovered from the toxic effects (except alopecia) to grade 2 or better from systemic anti-cancer therapy according the National Cancer Institute-Common Terminology Criteria for Adverse Events (NCI-CTCAE) Version 4.03 (or newer).

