APPENDIX 1: DETERMINATION OF TUMOR RESPONSE

Tumor response will be determined using RECIST v1.1 (Table 7) for subjects who enroll in the study with evidence of target and/or non-target lesions (Eisenhauer 2009). For subjects with NED at study entry RECIST v1.1 will be used such that the appearance of any new malignant lesion will be defined as PD, and no new lesions will be defined as SD as outlined in Table 8. Subjects with symptomatic deterioration will be documented as having had an event of PD as of the date the symptomatic deterioration was determined by the investigator.

Table 7 Time Point Response: Subjects with Target (+/- non-target) Disease

Target Lesion	Non-Target Lesion	New Lesion	Overall Response
CR	CR	No	CR
CR	Non-CR/non-PD	No	PR
CR	Non-evaluated	No	PR
PR	Non-PD or not all evaluated	No	PR
SD	Non-PD or not all evaluated	No	SD
Not all evaluated	Non-PD	No	NE
PD	Any	Yes or No	PD
Any	PD	Yes or No	PD
Any	Any	Yes	PD

CR – completed response; PR = partial response; SD = stable disease; PD = progressive disease; NE = inevaluable

Table 8 Disease Response Assessment on Study for Subjects with no Evidence of Disease at Study Day 1

Baseline		Post Day 1 Response Assessment			Overall Response
Target lesion	Non-Target lesion	Target lesion	Non-Target lesion	New Lesions	
Absent	Absent	Any	Any	New	PD
Absent	Absent	Absent	Absent	None	SD

PD = progressive disease; SD = stable disease

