## 6.1 ITT Set

The ITT set consists of all subjects randomized. All analyses of this set will be based on the randomized treatment arm to which the subjects are assigned. Efficacy analyses performed in the ITT set will be considered to be the primary indicator of efficacy.

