## 6.2 EE Set

The EE set consists of all subjects without major protocol violations, who have received at least 1 dose of study treatment, and have the baseline and at least 1 post-baseline tumor assessments available. The EE set will be analyzed according to the treatment received. Efficacy analyses performed in the EE set will be considered to be supportive.

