### 8.2.3.3 Objective Response Rate (ORR)

ORR will be estimated using the ITT set and EE set by both investigator's and IRC response assessment, the percent of subjects will be provided along with their corresponding 2-sided the 95% exact CI using Clopper-Pearson method. Also the best overall tumor response (CR, PR, SD, PD and not evaluable) will be tabulated with 2-sided 95% CI in the same table.

Also, ORR will be compared between treatment arms using a logistic regression. Logistic regression will be performed with the treatment arm and all stratification factors as independent variables. Treatment arm will be compared using the likelihood ratio chi-square test.

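### ORR is divided by all subjects although those with no disease at baseline cannot respond, and the plan does not say how subjects already in CR are scored

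*SAP*

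**What the plan says.** **Denominator.** SAP 5.1.2.3 gives "ORR = (CR+PR)/total number of subjects". SAP 8.2.3.3 adds that "ORR will be estimated using the ITT set and EE set by both investigator's and IRC response assessment", with Clopper-Pearson intervals. For ITT, SAP 6.1 states: "The ITT set consists of all subjects randomized". For EE, SAP 6.2 asks that subjects "have the baseline and at least 1 post-baseline tumor assessments available", along with dosing and compliance conditions. Neither set requires a lesion at baseline.

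**Who can respond.** Protocol 4.2, criterion 4: "Subjects with NED are eligible". Protocol Appendix 1 has two response tables. Table 7, the only one that yields CR or PR, is introduced as being "for subjects who enroll in the study with evidence of target and/or non-target lesions". For subjects with NED at study entry, "the appearance of any new malignant lesion will be defined as PD, and no new lesions will be defined as SD" (Table 8). Footnote g of the screening schedule, in both documents, makes the scan after first-line therapy the baseline for efficacy.

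**Model.** CR/NED against SD/PR is a randomization factor (SAP 3.3.1). SAP 8.2.3.3: "Logistic regression will be performed with the treatment arm and all stratification factors as independent variables". The arms are then compared by a likelihood ratio chi-square test.

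**The concern.** A response rate is usually read as the proportion of subjects with disease whose disease shrank or disappeared. Here the denominator includes subjects with nothing to shrink. The published rate and its interval therefore depend on how many subjects entered without disease, which says nothing about the vaccine. The group is expected to exist: eligibility admits subjects after resection or other local regional therapy, and CR/NED is a level of a stratification factor.

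There is also a gap. Table 8 is assigned by name to NED subjects only. A subject in CR at the Screening baseline has no lesion on that scan, which matches the absent baseline lesions in Table 8, but no sentence says so. Depending on which table a site uses, the same subject is either a certain non-responder or a certain responder.

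Finally, the CR/NED factor is a covariate in the ORR model. If nobody at that level can respond, its coefficient cannot be estimated, and the SAP gives no rule for that case in the ORR model.

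**Working it through.** The plan states no ORR rate, power or CR/NED share, so there is no ORR figure to reproduce. From the documents: 248 subjects, 124 per arm. Assumed throughout: the CR/NED share *f* and the response rates among subjects with lesions.

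**1. Dilution if Table 8 governs both NED and CR.** Reported ORR = (1 − *f*) × ORR among subjects with lesions.

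| Assumed *f* | 10% ORR reads as | 15% vs 5% reads as |
|---|---|---|
| 10% | 9% | 13.5% vs 4.5% |
| 20% | 8% | 12% vs 4% |
| 30% | 7% | 10.5% vs 3.5% |

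In whole subjects, with 25 CR/NED and 99 SD/PR per arm and 15 vs 5 responders:
- All subjects: 15/124 = 12.1% vs 5/124 = 4.0%, a difference of 8.1 points.
- SD/PR subjects: 15/99 = 15.2% vs 5/99 = 5.1%, a difference of 10.1 points.

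**2. Inflation if Table 7 is applied to baseline CR.** The first row of Table 7 (target CR, non-target CR, no new lesion) returns CR. SAP 5.1.2.3 takes the best response recorded after randomization and requires no confirmation. With *c* the share of the CR/NED group that is in CR, and assuming each such subject has a first on-study scan with no new lesion, reported ORR = (1 − *f*) × ORR + *f* × *c*. With *f* = 20% and *c* = 50%:
- 0.8 × 10% + 10% = 18%, where Table 8 would give 8%.
- For 15% vs 5%: 0.8 × 15% + 10% = 22% vs 0.8 × 5% + 10% = 14%.

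**3. The logistic model under the Table 8 reading.** The counts from step 1 were fitted by maximum likelihood with arm and the tumor-response factor. The other two factors were left out of this illustration.

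| Fit | Odds ratio for arm | LR chi-square | p (2-sided) |
|---|---|---|---|
| All subjects, with the factor | 3.36 | 5.79 | 0.016 |
| SD/PR subjects only | 3.36 | 5.79 | 0.016 |
| All subjects, without the factor | 3.28 | 5.67 | 0.017 |

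In the first fit the CR/NED coefficient had reached −34 when the optimizer stopped; it has no finite maximum. The arm result still equals the SD/PR-only result. As that coefficient falls, each CR/NED subject's fitted probability goes to zero and so does that subject's log-likelihood contribution, with or without arm in the model. The same argument holds when the other two factors are added.

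**4. Power under the Table 8 reading.** Two-proportion power at 1-sided 0.025, for 15% vs 5% among subjects with lesions and *f* = 20%: 64.3% using all subjects (12% vs 4%, 124 per arm) and 65.3% using SD/PR subjects only (about 99 per arm).

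**The case against.** The case for leaving the plan alone is substantial.

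- All randomized subjects form the declared primary efficacy set, and an all-randomized ORR is a legitimate, conservative summary that is openly defined. This stands, and is why that rate should be kept as a supportive row. It does not make it a good main estimate of response.
- Randomization is stratified on CR/NED, so dilution is expected to be equal in both arms and does not bias the comparison. This stands.
- ORR is outside the TTNT-DMFS testing sequence (SAP 8.2.3), and Protocol 1.1.2 says rapid shrinkage is not expected with this product. Both stand and limit the weight of the point.

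Two stronger readings are tempting, and the documents do not support them.

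- A reader might infer that all CR/NED subjects are barred from responding by definition. The rule limiting outcomes to SD or PD names NED only. For baseline CR it is an inference from the absent-lesion baseline in Table 8 and the choice of the screening scan as baseline. Under Table 7 the error runs the other way, the CR/NED level contains events, and there is no separation.
- A reader might infer that separation spoils the ORR comparison. The planned test is a likelihood ratio test for arm, which step 3 shows is unchanged. Only a nuisance coefficient diverges, with software warnings and unusable Wald output for that term. The SAP plans no inference on it.

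**Conclusion.** The point holds as a matter of reporting and definition. Following the plan as written, the ORR and its interval are diluted by the factor (1 − *f*) for subjects who cannot respond: 1 to 3 points on a 10% rate at an assumed no-disease share of 10% to 30%. The documents do not give the true share, so the actual size is unknown.

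The scoring of baseline CR is unsettled and matters more for the reported rate. In the assumed example (20% CR/NED, half in CR, 10% true rate) it moves the result from 8% to 18%. Neither figure is the response rate in subjects with disease.

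If Table 8 governs both groups, the arm test is unaffected, the comparison is unbiased and power is almost unchanged. Those assurances were checked for that reading only. PFS and OS error control is not touched under either. This is a worthwhile clarification at low cost, not a threat to the trial's conclusions.

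**What to change.** In SAP 5.1.2.3 and 8.2.3.3:

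1. Define the main ORR in randomized subjects with any target or non-target lesion (or both) at the Screening baseline, analysed as randomized. Do not limit it to target lesions: the introductory text of Appendix 1 also places subjects with only non-target disease among those assessed by Table 7, although that table's caption is narrower.
2. State that subjects with no lesion at that baseline, whether NED or CR, are assessed by Table 8 and are not counted as responders. Put the same sentence in Appendix 1 at the next protocol amendment.
3. Omit the tumor-response factor from the ORR logistic model. It is constant or nearly constant in the new population. Keep the other two factors and the likelihood ratio test.
4. Keep the all-ITT rate as a supportive row.

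The cost is SAP wording and a smaller stated ORR denominator. No data collection changes.

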Safety will be monitored by evaluating the frequency and severity of adverse events (AEs), serious adverse events (SAEs), clinical laboratory abnormalities, immunogenicity and persistence of LV305. Local laboratory test values will be used for treatment decisions and subject care; central laboratory test values will be used in the analysis of safety.

In addition, at only select US sites, the following will be collected:

Peripheral blood samples for the anti-NY-ESO-1 T cell and antibody assays will be obtained prior to start of study treatment from subjects on Day 1, Day 92, and Day 365 for subjects who have not had a progression event. A tumor biopsy will be obtained at screening, Day 92, and Day 365 for subjects who have not had a progression event. An additional tumor biopsy at time of progression event will be encouraged.

3.1.4 Post-treatment Period (For Subjects Who Discontinue Study Treatment for Reasons Other Than Disease Progression)

The Post-treatment period will begin at the end of treatment and will continue until investigator-determined radiographic PD (using RECIST v1.1) is documented.

Subjects will continue to undergo imaging until the time of disease progression. At the time of disease progression, subjects will enter the Long-term Follow-up period.

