6.3.1.3 Imaging During Treatment to the Time of Disease Progression

Tumor imaging assessments will be performed and evaluated every 8 weeks after Day 1 until investigator-determined PD (using RECIST v1.1) is documented. Disease progression will be assessed by the investigator using RECIST v1.1. For each subject, the images obtained during the Treatment period must have been collected using the same imaging method for all images during the Pre-screening and Screening periods. Subjects who have a global deterioration of health status that is attributed to progressive disease and leads to discontinuation of study treatment, but who are unable to provide radiographic evidence of disease progression (symptomatic deterioration), will be considered as having PD at the time of documented global deterioration of health for the purpose of determining PFS. Radiographic images (e.g., CT scan or MRI) will also be submitted to an IRC for storage and will be available for evaluation by a central reader, if requested by the sponsor. Details for the collection and evaluation of radiographic images are included in the Radiology Manual.

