7.7 Efficacy Analysis

7.7.1 Primary Efficacy Analyses:

The 2 primary efficacy endpoints of PFS and OS will be compared between CMB305 and placebo. Overall survival is defined as the time from randomization to the date of death.

Progression-free survival by investigator's assessment is defined as the time from randomization to the investigator-determined (using RECIST v1.1) date of disease progression or death. Radiographic images will be collected and assessed using RECIST v1.1 until the time the subject begins a new line of treatment.

For the purpose of PFS analysis, any one of the following events, whichever occurs first, will be used:

- Disease progression per RECIST v1.1 (See Appendix 1 [Table 7 \[Eisenhauer 2009\]](#))
- Symptomatic deterioration (global health deterioration) as described by RECIST v1.1
- For subjects with NED at time of randomization, any new malignant lesion that occurs after randomization per RECIST v1.1 (See Appendix 1 [Table 8](#))

Otherwise, subjects who do not have disease progression or have not died will be censored at the date when the last tumor imaging assessment determines a lack of progression. If a subject begins a new anti-cancer therapy or has radiotherapy, surgery, or other local regional therapy at a lesion site prior to documented progression, the subject will be censored at the last assessment where the subject was documented as progression free prior to the intervention. For subjects with NED at study entry, the appearance of a new malignant lesion as per RECIST v1.1 is defined as an event of progression for the purpose of PFS analysis. Subjects with 2 or more missing

response assessments (except for subjects with symptomatic deterioration) prior to a visit with documented progression (or death) will be censored at the last visit where the subject was documented to be progression free. PFS, by investigator's assessment, will be the primary PFS analysis. PFS by independent radiological review will be the supportive analysis.

The null hypothesis of no difference in OS/PFS between CMB305 and placebo, will be tested using a stratified log-rank test stratified by: disease status at screening (locally advanced unresectable versus metastatic), tumor response during screening (PR/SD versus CR/ NED), and by baseline presence of anti-NY-ESO-1 antibody (yes versus no)).

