**Table 3: Censoring Rules for PFS Analysis**

Situation	Date of Censoring	Outcome
No investigator-determined PD or death at the time of study discontinuation	Date of last adequate tumor assessment with no evidence of PD on or before study discontinuation	Censored
Investigator-determined PD or death after 2 or more consecutive missed tumor assessments	Date of last adequate tumor assessment with no evidence of PD that is before the first missed assessment	Censored
Investigator-determined PD or death after the start of subsequent intervention	Date of last adequate tumor assessment with no evidence of PD that is before the first subsequent intervention	Censored
No baseline and/or adequate post baseline tumor assessments or death at time of study discontinuation	Date of randomized	Censored

\* Adequate tumor assessment: tumor assessments with CR, PR, or SD as overall tumor response.

PFS by independent radiological review, if required, will be the supportive endpoints and follow similar definition and censorship as PFS by investigator's assessment, except that only PD from independent radiological review will be included as PD (symptomatic deterioration and clinical PD will not be included as PD).

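### Best overall response has no cut at a subsequent intervention, so a response that follows local therapy without PD could be credited to study treatment

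*SAP*

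**What the plan says.** **Response rule.** SAP 5.1.2.3 defines best overall response as the best "among all overall responses recorded from randomization until the last radiographic tumor assessment". Its one exclusion is "All tumor assessments after the first PD will be ignored". It also states: "No confirmatory measurement for CR or PR is required in this study". SAP 8.2.3.3, the ORR analysis, adds no further cut.

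**PFS rule.** For PD or death after a subsequent intervention, SAP Table 3 sets the censoring date as "Date of last adequate tumor assessment with no evidence of PD that is before the first subsequent intervention". The SAP describes the term under TTNT: "Subsequent intervention includes anticancer therapy, cancer-related surgery and local regional therapy".

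**When imaging stops.** The protocol gives two accounts.
- Protocol 7.7.1, repeated in the synopsis: "Radiographic images will be collected and assessed using RECIST v1.1 until the time the subject begins a new line of treatment".
- Protocol 3.1.4, for subjects who leave treatment without PD: "Subjects will continue to undergo imaging until the time of disease progression". Protocol 6.3.1.3 agrees: "Tumor imaging assessments will be performed and evaluated every 8 weeks after Day 1 until investigator-determined PD". Footnote c of Table 2 also runs post-treatment scans to progression. Neither these sections nor the footnote mentions a new line of treatment.

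The SAP reproduces footnote c in its own Table 2. It does not carry over the new-line limit from Protocol 7.7.1.

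**The concern.** The SAP treats a subsequent intervention as the end of informative follow-up for PFS but not for response. The same subject could be censored for PFS at the last scan before a resection or ablation, then enter ORR as a CR or PR on a scan taken after it. With no confirmation required, one such scan is enough.

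The plan expects these cases: Protocol 7.7.1 gives a PFS rule for radiotherapy, surgery or other local therapy before documented progression. Local therapy is also common in this disease. Protocol 1.1.3 cites an observational study in which 49% of subjects had some local regional treatment of metastases, although that is not a rate before PD on study.

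At stake is what ORR means. Protocol 1.1.2 does not expect rapid tumor shrinkage from CMB305, so true responses may be few and a handful of procedure-related ones could make up much of the observed rate.

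**Working it through.** The documents give no assumed ORR, power or sample size for ORR, so there is no planned figure to reproduce. The check is a reading of the rules, followed by scale under stated assumptions.

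**1. Which routes are open?**

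| Situation | What the documents do | Can it add a response? |
|---|---|---|
| New systemic drug line before PD | Protocol 7.7.1 stops image assessment at the new line | Largely no, if followed; the SAP rule itself does not exclude it |
| Any intervention after RECIST PD | SAP 5.1.2.3 drops later scans | No |
| Intervention after symptomatic deterioration | Counted as PD (Protocol Appendix 1), so later scans drop | No |
| NED at entry | Only SD or PD possible (Protocol Table 8) | No |
| Local therapy during study treatment, no PD | Prohibited by Protocol 5.8.2 | Only as a deviation |
| Local therapy after study treatment ends, no PD, scans continue | Protocol 5.8.2 can be read as having ended; 3.1.4, 6.3.1.3 and Table 2 footnote c continue imaging to PD | Yes, under the SAP rule |

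Protocol 7.7.1 names radiotherapy, surgery and local regional therapy separately from new anti-cancer therapy. A resection or ablation therefore need not count as a new line of treatment.

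**2. Effect of one subject.** With 124 subjects per arm (SAP 4), 1/124 = 0.81 percentage points. If the underlying ORR were 5% and three subjects were affected (both assumptions), ORR would be 5% + 3/124 = 5% + 2.4 = 7.4%.

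**3. Range for one arm.** Let *f* be the share of an arm with an intervention before PD and continued scans, and *r* the share of those then read as CR or PR. Neither is in the documents. The rise in ORR is *f* × *r*.
- Low: 0.02 × 0.20 = 0.4 points (0.5 subjects)
- Middle: 0.05 × 0.50 = 2.5 points (3.1 subjects)
- High: 0.10 × 0.50 = 5.0 points (6.2 subjects)

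**4. Between-arm comparison.** SAP 8.2.3.3 uses a likelihood ratio chi-square. The table below uses the unstratified version, 2 × [ℓ(a) + ℓ(b) − ℓ(a+b)], with *a* and *b* responders in arms of 124 and ℓ the binomial log-likelihood at the observed proportion (pooled over 248 for the last term). For 3 versus 0 it is 2 × (−14.13 + 16.23) = 4.2, p = 0.04. The worst case puts all extra responses in one arm:

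| True responders in each arm | Extra in one arm for two-sided p < 0.05 | p |
|---|---|---|
| 0 | 3 | 0.041 |
| 2 | 6 | 0.045 |
| 4 | 8 | 0.035 |
| 6 | 9 | 0.037 |
| 12 | 11 | 0.043 |

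**5. Could exposure differ by arm?** Take the plan's PFS assumptions (placebo median 4 months, HR 0.55, so 4/0.55 = 7.27 months on CMB305) and add exponential times. The share free of PFS events at 12 months, when treatment ends, is 0.5^(12/4) = 12.5% on placebo (15.5 of 124) and 0.5^(12/7.27) = 31.9% on CMB305 (39.5 of 124). If the assumed PFS effect is real, the pool in which this could happen is about 2.5 times larger on CMB305 (39.5/15.5). The pool includes NED subjects, who cannot contribute, and the documents do not say how many of the rest would have an intervention.

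**The case against.** The strongest reply is that the protocol already closes most of the gap. Image assessment ends at a new line of treatment, other anti-cancer therapy is prohibited on treatment, scans after PD are dropped, and NED subjects cannot respond. The sections that continue imaging to PD can be read as general schedules, subject to the narrower sentence in 7.7.1. This largely stands for drugs. A reader might infer from the SAP wording alone that responses to later systemic therapy will be counted; the documents do not support that if Protocol 7.7.1 is followed. It does not stand for local therapy, for the reasons in the working. SAP 9, which lets the SAP prevail over the protocol's statistical text, is a further reason to have the cut in the SAP.

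A second reply is that nothing shows a treated lesion would be scored as CR or PR. Protocol Table 7 has an inevaluable outcome when not all target lesions are evaluated, and detailed image-evaluation rules are in a Radiology Manual that is not among the documents. This stands. The point is that such a response could be credited, not that it will be.

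A third reply is that the trial is double-blind, so local therapy has no stated reason to differ by arm. That is fair for the decision to intervene. It does not ensure equal exposure if one arm stays PD-free longer.

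Finally, using different scans for PFS and ORR is not an error in itself. That is true; the issue is attribution of the response.

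**Conclusion.** The gap is real but narrow. As written, SAP 5.1.2.3 would count an unconfirmed CR or PR recorded after surgery, radiotherapy or other local regional therapy in a subject without PD, although PFS for that subject is cut before the procedure. The main case is after study treatment ends while imaging continues.

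The size is 0.8 points of ORR per affected subject, or 0.4 to 5.0 points for an arm over the assumed range. Those shares, any baseline ORR such as 5%, and the scoring of treated lesions as responses are all assumptions. The p-value thresholds are worst cases with every extra response in one arm.

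A reader might also infer a threat to the trial's type I error. The documents do not support that: neither primary endpoint uses best overall response, and ORR is outside the TTNT-then-DMFS sequence. Only the interpretation of a secondary endpoint is affected, so this is a desirable clarification and not a condition for the primary analysis.

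**What to change.** In SAP 5.1.2.3, replace the response window with: *recorded from randomization until the earliest of first PD, the start of the first subsequent intervention (as defined in SAP 5.1.2.1), and the last radiographic tumor assessment*.

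This matches Table 3 and uses the SAP's existing definition. It also gives the independent-review version of ORR a rule to follow: that text now refers back to ORR censorship, which the section does not define. The cut is somewhat wider than the protocol's PFS wording, which limits local therapy to a lesion site, but it is the same cut the SAP applies to PFS.

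Separately, Protocol 7.7.1 must be reconciled with 3.1.4, 6.3.1.3 and Table 2 footnote c on when imaging stops, so that sites and the analysis follow one account.

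The SAP change is one sentence, needs no data beyond the intervention dates already used for PFS and TTNT, and should be made before database lock. The downside is a possibly slightly lower reported ORR.
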